# **Outcomes of Metabolic Resuscitation Using Ascorbic Acid, Thiamine, and Glucocorticoids in the Early Treatment of Sepsis.**

## **ORANGES Trial**

**NCT#: NCT03422159**

### **Background and Significance:**

The global burden of sepsis is substantial with an estimated 15 to 19 million cases per year; the vast majority of these cases occur in low income countries. [1] With more timely diagnosis and improvement in supportive care the 28-day mortality from sepsis in high income countries has declined to about 25%, however, the mortality from septic shock remains as high as 45%. [2,3] Moreover, the mortality from sepsis and septic shock in low income countries is reported to be as high as 60%. [4-6] In addition to short term mortality, septic patients suffer from a numerous short- and long-term complications and are at an increased risk of death for up to five years following the acute event. [7] Over the last 3 decades over 100 phase II and phase III clinical trial have been performed testing various novel pharmacologic agents and therapeutic intervention in an attempt to improve the outcome of patients with sepsis and septic shock; all of these studies have failed to show an improvement in patient outcomes. [8] New therapeutic approaches to sepsis are desperately required; considering the global burden of sepsis these interventions should be effective, cheap, safe and readily available.

A large body of experimental data has demonstrated that both corticosteroids and intravenous vitamin C reduce activation of nuclear factor KB (NFKB) attenuating the release of pro-inflammatory mediators, reduce the endothelial injury characteristic of sepsis thereby reducing endothelial permeability and improving macrocirculatory flow, augment the release of endogenous catecholamines and enhance vasopressor responsiveness. [9-16] In animal models these effects have resulted in reduced organ injury and increased survival. Corticosteroids have been evaluated in several clinical trials, with meta-analysis of these trials demonstrating somewhat conflicting outcomes. [17-20] Low-dose stress corticosteroids have proven to be safe with no increased risk of clinically important complications. [17] While corticosteroids decrease vasopressor dependency the effect on survival is less clear. [19,21]

Several studies have investigated the use of intravenous vitamin C in critically ill patients. Nathens et al randomized 595 surgical ICU patients (91% trauma patients) to receive intravenous vitamin C and vitamin E for up to 28 days. [22] The vitamin combination was associated with a significant reduction in the incidence of multiple system organ failure ( $p=0.04$ ) with a trend to reduced mortality and length of ICU stay. No adverse effects were noted with the vitamin combination. Fowler et al performed a pilot

study in 24 patients with severe sepsis and septic shock. [23] In this study patients were randomized to placebo (n=8), low dose intravenous vitamin C (50 mg/kg) (n=8) or high dose vitamin C (200mg/kg). Vitamin C attenuated the inflammatory response with both doses of the vitamin being devoid of any side effects. Although the Sequential Sepsis Related Organ Failure Score (SOFA) fell significantly in both treatment arms the study was underpowered to determine any outcome benefit. Zabet and colleagues performed a RCT in which they evaluated the role of intravenous vitamin C in a dose of 100 mg/kg/day (about 7g/day) in 28 surgical ICU patients with septic shock. [24] In this study the mean dose of norepinephrine and duration of norepinephrine administration were significantly lower in the ascorbic acid than the placebo group. The 28-day mortality was significantly lower in the ascorbic acid than the placebo group (14% vs. 64%, p = 0.009). No side effects related to the vitamin C infusion were reported. Tanaka et al randomized 37 patients with severe burn to very high dose vitamin C (about 110g/day) or placebo.[25] Patients who received vitamin C required less fluid resuscitation with a trend towards reduced length of stay and mortality. No adverse effects were noted with the very high dosages of vitamin C. Several studies have administered vitamin C in doses exceeding 100g/day as adjuvant therapy in patients with cancer with no discernable side effects. [26-33] Vitamin C appears to be toxic to normal human cells (not cancer cells) at a concentration on greater than 25 mM. [33] A dose of 6g/day will achieve a steady state serum concentration of about 240uM [34-36] which is about 100 times less than the dose required to cause cellular toxicity. The package insert for vitamin C [37] lists no contraindications or adverse effects of the drug and states that as much as “6 grams has been administered without evidence of toxicity”. The only reported restriction to the use of high dose intravenous vitamin C is in patients with known glucose-6-phosphate deficiency (G6PD) in whom hemolysis has been reported. [38,39] It is important to recognize that patients with sepsis predictably have very low serum vitamin C levels, which can only be corrected with intravenous vitamin C in a dose of more than 3gm per day. [23,34,36] The low or undetectable levels of vitamin C likely result from the metabolic consumption of the molecule as well as increased renal losses. Furthermore, unlike all other mammals, primates and guinea pigs are unable synthesize vitamin C is due to mutations in the L-gulonolactone oxidase (*GLO*) gene which codes for the enzyme responsible for catalyzing the last step of vitamin C biosynthesis. [40] In almost all species, except humans and guinea pigs, vitamin C production increases during stress and is secreted by the adrenal gland; in these species vitamin C is best considered a stress “hormone”. [40] Vitamin C is an essential cofactor for the production of corticosteroids and catecholamines by the adrenal gland. [13,41] Vitamin C has been shown to reverse adrenal suppression caused by induction doses of etomidate during anesthesia.[42,43]

Ascorbate donates a single electron in all its redox reactions, generating the ascorbate radical. This radical is not very reactive with anything but itself. Dismutation of two ascorbate radicals forms a molecule each of ascorbate and dehydroascorbate. Hydrolysis of the lactone ring of dehydroascorbate

irreversibly converts it to 2,3-diketo-1-gulonic acid which is then converted to oxalate. Oxalate is normally excreted by the kidney and serum levels will increase with renal impairment. In patients with renal impairment receiving mega-dose vitamin C, supersaturation of serum with oxalate may result in tissue deposition as well as crystallization in the kidney. [44,45] Glyoxylate, a byproduct of intermediary metabolism, is either reduced to oxalate or oxidized to CO2 by the enzyme glyoxylate aminotransferase; thiamine pyrophosphate is a co-enzyme required for this reaction. [46] Thiamine deficiency increases the conversion of glyoxylate to oxalate resulting in hyper-oxalosis. [47,48] Donnino and colleagues have demonstrated that thiamine deficiency is common (32%) in patients with sepsis and that treatment with thiamine in these patients reduces mortality. [49] In a post-hoc analysis of this study these authors demonstrated that thiamine decreased the risk of acute kidney injury and the required for renal replacement therapy in all treated patients. [50]

It has previously been suggested that *“...the best hope for therapeutic advances [in sepsis] will depend on broad-base targeting, in which multiple components are targeted at the same time.”*[51] Such combination “chemo-therapy” targeting multiple biological pathways is the standard approach in the treatment of malignant disease. While the benefits of vitamin C, hydrocortisone, and thiamine alone are likely limited,[23,49,50,52] we believe that these medications act synergistically to reduce the risk of organ failure and death in patients with sepsis. This hypothesis is supported previous research [53,54] and more recently a set of elegant experiments performed by Barabutis et al. [55] Using a validated pulmonary endothelial monolayer model, these authors demonstrated that hydrocortisone together with vitamin C protected the vascular endothelium from damage by endotoxin while neither agent alone had this effect. Previous research has demonstrated that vitamin C reverses oxidation of the glucocorticoid receptor (GR) a likely manifestation of sepsis.[53] Oxidation of the GR limits binding of the GR to both ligand and DNA responsive units decreasing the activity of glucocorticoids. [53] Furthermore, glucocorticoids increase the expression of the sodium vitamin C transporter-2 (SVCT-2) which is an essential transport protein necessary for vitamin C to be transported intracellularly.[54]

We therefore propose that a “metabolic resuscitation protocol” including vitamin C, corticosteroids and thiamine will limit the development of organ failure and reduce mortality in patients with severe sepsis and septic shock. This postulate is supported by the preliminary findings by Marik et al. [56] In a retrospective before-after clinical study, these authors compared the outcome and clinical course of consecutive septic patients treated with intravenous vitamin C, hydrocortisone and thiamine during a 7-month period (treatment group) compared to a control group treated in during the preceding 7 months.[56] The primary outcome was hospital survival. A propensity score was generated to adjust the primary outcome. There were 47 patients in both treatment and control groups with no significant differences in baseline characteristics between the two groups. The hospital mortality was 8.5% (4 of 47)

in the treatment group compared to 40.4% (19 of 47) in the control group ( $p < 0.001$ ). The propensity adjusted odds of mortality in the patients treated with the vitamin C protocol was 0.13 (95% CI 0.04-0.48,  $p=0.002$ ). The SOFA score decreased in all patients in the treatment group with none developing progressive organ failure. Vasopressors were weaned off all patients in the treatment group, a mean of  $18.3 \pm 9.8$  hours after starting treatment with vitamin C protocol. The mean duration of vasopressor use was  $54.9 \pm 28.4$  hours in the control group ( $p < 0.001$ ). The results of this study provide sufficient information for the design of an adequately powered, pragmatic randomized controlled trial.

### **Study Design:**

#### ***Specific Aims of the Study:***

The aim of this study is to determine the effect of the combination of intravenous vitamin C, hydrocortisone and thiamine on the clinical course and outcome of patients with sepsis and septic shock.

This study will be performed at Community Medical Center and Monmouth Medical Center Southern Campus. All patients admitted to the ICU with the primary diagnosis of sepsis or septic shock will be screened for inclusion into this study. The diagnosis of sepsis and septic shock will be based on the 2016 Surviving Sepsis Campaign definitions.[63]

#### ***Inclusion Criteria:***

- i. Diagnosis of sepsis or septic shock within 12 hours of admission to the ICU
- ii. Informed consent as dictated by IRB and local practice.
- iii. Compliance with the 3 hour sepsis bundle
  - 30ml/kg of intravenous crystalloid fluid (e.g.: sodium chloride 0.9%) for lactic acid  $>4$  and/or systolic blood pressure  $<90$ mmHg / mean arterial pressure  $<65$ mmHg
  - Lactic acid level drawn
  - Broad spectrum antibiotics given after obtaining blood cultures

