#### ***Exclusion criteria:***

- i. Age  $< 18$  years
- ii. Pregnant

- iii. DNR/DNI with limitations of care on admission
- iv. Patients with terminal end stage disease (i.e. stage IV cancer, end stage heart failure) that are unlikely to survive to hospital discharge
- v. Patients with a primary admitting diagnosis of an acute cerebral vascular event, acute coronary syndrome, active gastrointestinal bleeding, burn or trauma [64-66]
- vi. Requirement for immediate surgery [64-66]
- vii. Patients with HIV and a CD4 < 50 mm^2 [64-66]
- viii. Patients with known glucose-6 phosphate dehydrogenase (G-6PD) deficiency.[39]
- ix. Patients with sepsis/septic shock transferred from another hospital
- x. Patients with features of sepsis/septic shock > 24 hours after admission

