**Study end-points:**

***Primary end-point***

- i. Time to vasopressor independence. Defined as the time from starting the active treatment/placebo to discontinuation of all pressors
- ii. Delta SOFA score, defined as the initial SOFA score minus the day 4 SOFA score

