**Power Calculation:**

Based on the results of the preliminary study of Marik et al we project that the combination of hydrocortisone, vitamin C and thiamine could reduce time to vasopressor discontinuation from 54 (+/- 30 hours) versus 30 hours. For the additional primary outcome we projected a greater change of SOFA score of 4 (+/- 3) versus 2. Assuming a type 1 error of 5% (alpha of 0.05) and a power of 80% (the ability to detect a difference between two groups when a difference exists) would require a sample size of 94 patients. To account for dropouts and patients not requiring vasopressor therapy we will therefore aim for a sample size of 140 patients.

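### Eligibility limits the time to diagnosis but not the time to randomisation or first dose, and the 54 h control planning figure appears to run on a different clock from primary end-point i.

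*Protocol*

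**What the plan says.** The Protocol title describes the regimen as "Glucocorticoids in the Early Treatment of Sepsis". Two eligibility rules mention time. Inclusion i requires "Diagnosis of sepsis or septic shock within 12 hours of admission to the ICU". Exclusion x removes "Patients with features of sepsis/septic shock > 24 hours after admission", without saying whether the admission is to hospital or to the ICU. The screening text gives no time limit. The dosing section gives frequency and a four-day course but no window for starting.

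Primary end-point i is "Defined as the time from starting the active treatment/placebo to discontinuation of all pressors". The other primary end-point is "Delta SOFA score, defined as the initial SOFA score minus the day 4 SOFA score", which makes no reference to first dose.

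The Power Calculation, the same in Protocol and SAP, projects that the regimen "could reduce time to vasopressor discontinuation from 54 (+/- 30 hours) versus 30 hours". It gives no time origin for either value. The Protocol's Background section supplies the likely source. In the preliminary study's control group, "The mean duration of vasopressor use was" 54.9 h (SD 28.4). The treated group's 18.3 h (SD 9.8) is counted in "hours after starting treatment with vitamin C protocol". The Data Collection list keeps the two quantities apart: item ix is duration of vasopressor use, and item x is time to independence from first dose.

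**The concern.** A limit on when sepsis is diagnosed does not limit when treatment starts. If enrolment can come well after diagnosis, a patient may have spent much of the vasopressor course before the end-point's clock begins. Less time then remains for treatment to shorten, and patients already off pressors at first dose cannot be assessed for end-point i.

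The planning figures add to this. The end-point measures both arms from first dose, but 54 h looks like a whole vasopressor course. The placebo arm would be expected to average 54 h only if dosing began about when pressors began. With longer delay, the true difference could be smaller than the planned 24 h, and a null result could reflect late dosing as much as an ineffective regimen.

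**Working it through.** **Timing rules side by side.** Exclusion x has three possible readings.

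- Onset after ICU admission: it removes nobody whom the 12 h diagnosis rule has not already removed.
- Onset after hospital admission: it limits onset, not enrolment.
- Still septic more than 24 h after admission: it caps enrolment near 24 h, but still does not limit first dose.

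A patient diagnosed at ICU hour 2 and consented at hour 60, still on a pressor, passes the timing rules under the first two readings and fails under the third.

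**Inputs.** From the Power Calculation: 54 and 30 h, SD 30 h, SOFA change 4 and 2 with SD 3, alpha 0.05, power 80%, 94 evaluable, 140 enrolled. From the Background: control duration 54.9 h, SD 28.4 h. Assumed because not stated: two-sided test, 1:1 allocation, and a delay D from pressor start to first dose that is equal for all patients.

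**The plan's own figure.** n per arm = 2(1.960 + 0.842)² × SD²/difference².

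- End-point i: 2 × 7.849 × 900/576 = 24.5, so 25 per arm, 50 in total.
- Delta SOFA: 2 × 7.849 × 9/4 = 35.3, so 36 per arm, 72 in total.

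Neither gives 94. That is a separate matter, and 94 (47 per arm) is taken as it stands. With no delay and a 24 h difference, 94 gives about 97% power for end-point i.

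**Remaining control time.** Let X be control pressor duration. Two shapes were simulated: a normal (54.9, 28.4) cut at zero, whose mean and SD after the cut are 56.7 and 26.5 h, and a gamma with mean 54.9 and SD 28.4 (shape (54.9/28.4)² = 3.74). The quantities are P(X ≤ D), the share already weaned, and E[X − D | X > D], the mean remaining time.

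**Difference.** The low case holds the treated arm at 30 h (remaining time − 30), which treats 54 h as counted from pressor start and 30 h from first dose. The high case assumes a proportional effect: remaining time × (1 − 30/54).

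**Power.** Φ(difference/(SD × √(2/47)) − 1.960). With SD 30, the standard error is 6.19 h.

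| D | Shape | Already weaned | Mean remaining (residual SD) | Low difference; power, SD 30 | High difference; power, SD 30 | High case; power, residual SD |
|---|---|---|---|---|---|---|
| 12 h | cut normal | 4.0% | 46.8 h (25.0) | 16.8 h; 77% | 20.8 h; 92% | 98% |
| 12 h | gamma | 1.5% | 43.6 h (28.0) | 13.6 h; 59% | 19.4 h; 88% | 92% |
| 24 h | cut normal | 11.4% | 38.2 h (23.0) | 8.2 h; 26% | 17.0 h; 78% | 95% |
| 24 h | gamma | 11.1% | 35.5 h (26.6) | 5.5 h; 14% | 15.8 h; 72% | 82% |

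Example (24 h, gamma, low): 5.5/6.19 − 1.960 = −1.07, and Φ(−1.07) = 14%.

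These powers hold 94 evaluable fixed. The step from 140 to 94 allows a loss of 1 − 94/140 = 33%. The weaned shares lie inside that, but the same allowance must also cover dropouts and patients never on pressors.

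**If the clocks agree.** If 54 and 30 h both run from pressor start and delay shifts both arms equally, the shift cancels and the difference stays 24 h, apart from patients weaned before dosing.

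**The case against.** The strongest reply is that the documents show no late dosing. They give no delay at all, and exclusion x may already cap enrolment at about 24 h. This stands in part. A reader might infer that patients do enter days into sepsis, but the text supports only that, under the onset readings, nothing prevents it. The ambiguity is itself a reason to reword the criterion, and no reading limits first dose.

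A second tempting inference is that both planning values count from pressor start, or that the clocks are proven to differ. The documents support neither. The 54 h figure matches a duration; the 30 h figure is not the source's 18.3 h, and its origin is unstated. The low end of the range depends on mixed clocks.

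Third, a reader might suppose that patients who wean quickly never enter the trial. Vasopressor use is not an inclusion criterion, so they remain eligible and can contribute to delta SOFA; they are lost only to end-point i.

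Fourth, it would go too far to say the trial is biased or cannot answer its question. Delay is balanced between blinded arms in expectation. The word early appears in the title, while the stated aim is the regimen's effect on clinical course and outcome. Under a proportional effect with residual SDs, power at 94 stays above 80% even at a 24 h delay. What remains is a gap in the plan and an unstated clock, with consequences that range from small to serious depending on facts the plan does not give.

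**Conclusion.** The point holds in a limited form. The plan sets no maximum time to randomisation or first dose, exclusion x does not clearly supply one, and the control planning value appears to be a total duration while end-point i runs from first dose.

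If all patients were dosed 12 h after pressor start, the planned 24 h difference would fall to about 14–21 h, with power of 59–92% at SD 30 h. At 24 h it would fall to about 5.5–17 h, with power of 14–78%. Using residual SDs raises the proportional-effect power to 92–98% and 82–95%. All these figures rest on an assumed uniform delay, two assumed distribution shapes and 94 evaluable patients; the width of the range is mainly the unstated origin of 30 h.

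The harm is dilution, and a null result that would be hard to interpret as a test of early treatment. It is not between-arm bias, and it concerns one of two primary end-points.

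**What to change.** 1. Add to eligibility a maximum interval from ICU admission or diagnosis to randomisation, and require first dose promptly after it. The investigators should set the length.
2. Reword exclusion x to name the admission and to say whether it limits onset or enrolment, and reconcile it with inclusion i.
3. Record the clock times of vasopressor start and first dose. Analyse end-point i with adjustment for pre-dose vasopressor time, set to zero if pressors start after first dose. This replaces the unadjusted t-test or Mann-Whitney comparison for that end-point. The covariate is fixed before any study drug is given, and for patients on pressors at first dose, items ix and x of Data Collection already yield it by subtraction.
4. In the Power Calculation of both documents, state the clock for 54 h and for 30 h, and restate the planned difference on the first-dose clock with a range for the assumed delay.

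The cost is a few lines of text, two time stamps, slightly slower recruitment because some late-identified patients become ineligible, and a model-based analysis for one end-point.

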#### ***Exclusion criteria:***

- i. Age  $< 18$  years
- ii. Pregnant

- iii. DNR/DNI with limitations of care on admission
- iv. Patients with terminal end stage disease (i.e. stage IV cancer, end stage heart failure) that are unlikely to survive to hospital discharge
- v. Patients with a primary admitting diagnosis of an acute cerebral vascular event, acute coronary syndrome, active gastrointestinal bleeding, burn or trauma [64-66]
- vi. Requirement for immediate surgery [64-66]
- vii. Patients with HIV and a CD4 < 50 mm^2 [64-66]
- viii. Patients with known glucose-6 phosphate dehydrogenase (G-6PD) deficiency.[39]
- ix. Patients with sepsis/septic shock transferred from another hospital
- x. Patients with features of sepsis/septic shock > 24 hours after admission

**Study end-points:**

***Primary end-point***

- i. Time to vasopressor independence. Defined as the time from starting the active treatment/placebo to discontinuation of all pressors
- ii. Delta SOFA score, defined as the initial SOFA score minus the day 4 SOFA score

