***Data Collection:***

The following de-identified demographic and clinical data will be collected.

- i. Age
- ii. Sex
- iii. Weight
- iv. Admitting diagnosis and possible site of infection
- v. Blood culture results
- vi. Co-morbidities, including diabetes, hypertension, cardiac failure, COPD, malignancy
- vii. Requirement for mechanical ventilation (Y/N).
- viii. Use of vasopressor agents (Y/N). The hourly dosage of vasopressors will be recorded as the norepinephrine equivalent dosage. [70,71]
- ix. Duration of vasopressor use
- x. Time to vasopressor independence from start of active drug/placebo
- xi. Daily urine output (for first 4 days)

xii. Fluid balance after 24 and 72 hours

xiii. Presence of acute kidney injury (AKI). Presence of AKI: Acute kidney injury (AKI) will be defined using the KDIGO criteria; namely, an increase of the s-creatinine > 0.3 mg/dl or a level > 1.5 times the baseline value. [27] If the baseline s-creatinine is not known a value > 1.5 mg/dl will be regarded as diagnostic of AKI.

xiv. Length of ICU and hospital stay

xv. ICU, hospital, and 28-day mortality

xvi. Routine laboratory data for 4 days including:

a. serum creatinine

b. white cell count (WBC)

c. platelet count

d. total bilirubin

e. PaO2/FiO2 ratio

f. Procalcitonin (PCT) – on days 1 and 4

g. lactate level

h. urine oxalate level (day 4)

xvii. HostDx Sepsis genetic testing (day 1) if consent is provided for additional sub-study.

xviii. The patients' admission APACHE II and APACHE IV scores will be recorded. The APACHE IV score allows calculation of the predicted hospital mortality and predicted ICU length of stay (LOS).

ix. The daily SOFA (Sepsis-related Organ Failure Assessment) score will be recorded for the first 4 treatment days.

The APACHE II score (incrementing score of 0-71) and APACHE IV score (incrementing score 0-286) are standardized measures of disease severity that are used to predict hospital mortality and ICU LOS.

[72,73] The SOFA score was designed to sequentially assess the severity of organ dysfunction in patients who are critically ill from sepsis (incrementing score 0-24). [74]. The SOFA scores is calculated 24 hours

after admission to the ICU and daily thereafter. SOFA scores that increase by about 30 percent are associated with a mortality of at least 50 percent.[75]

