Outcomes of Metabolic Resuscitation Using Ascorbic Acid, Thiamine, and Glucocorticoids in the Early Treatment of Sepsis.

ORANGES Trial

NCT#: NCT03422159

Document Date: May 13th, 2019

Study end-points:

Primary end-point

- i. Time to vasopressor independence. Defined as the time from starting the active treatment/placebo to discontinuation of all pressors
- ii. Delta SOFA score, defined as the initial SOFA score minus the day 4 SOFA score

Secondary end-points

- iii. 28-day mortality
- iv. Hospital mortality
- v. PCT clearance (PCT-c) calculated using the following formula: initial PCT minus PCT at 96 hours, divided by the initial PCT multiplied by 100. [67,68]
- vi. ICU mortality
- vii. ICU length of stay (LOS) and ICU free days. ICU free days is calculated as the number of days alive and out of the ICU to day 28
- viii. Hospital LOS

Power Calculation:

Based on the results of the preliminary study of Marik et al we project that the combination of hydrocortisone, vitamin C and thiamine could reduce time to vasopressor discontinuation from 54 (+/- 30 hours) versus 30 hours. For the additional primary outcome we projected a greater change of SOFA

score of 4 (+/- 3) versus 2. Assuming a type 1 error of 5% (alpha of 0.05) and a power of 80% (the ability to detect a difference between two groups when a difference exists) would require a sample size of 94 patients. To account for dropouts and patients not requiring vasopressor therapy we will therefore aim for a sample size of 140 patients.

Data analysis:

Summary statistics will be used to describe the clinical data and presented as mean \pm SD, median with interquartile range (IQR) or percentages as appropriate. Chi squared analysis with Fisher's exact test (when appropriate) and Student's t test (Mann Whiney U test for non- normal distributions) were used to compare data between the active treatment group and the placebo group with statistical significance declared for probability values of 0.05 or less.

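### Primary end-point i does not require a pressor to be running at first dose, so late starters are charged for pressor-free hours and post-randomisation pressor use can decide who has a value

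*Protocol*

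**What the plan says.** Protocol, Primary end-point (i): "Time to vasopressor independence. Defined as the time from starting the active treatment/placebo to discontinuation of all pressors". The SAP repeats the definition without adding a restriction: "Defined as the time from starting the active treatment/placebo to discontinuation of all pressors".

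Protocol, Inclusion Criteria (i), admits "Diagnosis of sepsis or septic shock within 12 hours of admission to the ICU". Vasopressor use is not a condition of entry.

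The only text that bears on who counts for this end-point is in the Power Calculation: "To account for dropouts and patients not requiring vasopressor therapy we will therefore aim for a sample size of 140 patients". It gives no time point for the need for pressors and does not split the allowance between the two kinds of loss. The projected effect is that treatment "could reduce time to vasopressor discontinuation from 54 (+/- 30 hours) versus 30 hours".

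Protocol, Data Collection, lists a yes/no item for vasopressor use with no time attached, an hourly vasopressor dosage record (item viii), "Duration of vasopressor use" and, separately, "Time to vasopressor independence from start of active drug/placebo". Duration of use is collected but is not an end-point. The Data analysis sections of both documents name a t test or Mann-Whitney test and define no analysis set. They give no rule for pressors started after the first dose and no value for patients who never receive one.

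**The concern.** The clock starts at the first dose for everyone, but the event that stops it exists only for patients who receive pressors. For a patient already on pressors at first dose, the score is time to come off them. For a patient who starts later, the score is the pressor-free lag plus the course. Two problems follow.

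- **Scoring.** The pressor-free hours of a late starter count as if they were dependence. A treatment that only postpones shock would worsen its own score.
- **Selection.** Nothing limits a value to patients on pressors at first dose, so starting pressors after randomisation can bring a patient into the comparison. The Protocol's background expects treatment to reduce the development of organ failure. If it does, treatment helps to decide who is compared, and randomisation does not protect that comparison.

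This is one of two primary end-points, and its population is not stated in either document. The choice between patients on pressors at first dose and patients ever on pressors could therefore be made after the data are seen.

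**Working it through.** **1. The plan's own figures.** End-point i: difference 54 - 30 = 24 h, SD 30 h, alpha 0.05 (two-sided assumed), power 80%, 1:1 allocation assumed.

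n per arm = 2 x (1.96 + 0.8416)^2 x 30^2 / 24^2 = 24.5, so 25 per arm and 50 in total (52 with the t distribution).

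Delta SOFA (difference 2, SD 3): 2 x (1.96 + 0.8416)^2 x 3^2 / 2^2 = 35.3, so 36 per arm and 72 in total (74 with t).

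Neither gives the stated 94. That is a separate matter and nothing below depends on it. The step from 94 to 140 implies a combined loss of 46/140 = 32.9%.

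**2. The scoring rule applied literally.** First dose at hour 0, pressors from hour 30 to hour 40: score 40 h, hours on pressors 10. This patient scores worse than the projected active-arm mean of 30 h.

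**3. Selection with no true effect on duration.** Assumptions, none of them in the documents:
- 47 per arm on pressors at first dose and 23 not (94 and 46 of 140);
- late starts uniform between 6 and 72 h, so mean onset 39 h;
- mean course 54 h, SD 30 h, in patients on pressors at first dose in both arms;
- late starts in 10% of the 23 on active (2.3 patients) and 40% on placebo (9.2 patients).

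Expected arm mean = (47 x 54 + late starters x late score) / (47 + late starters), where late score = 39 + mean late course.

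| Mean late course | Late score | Placebo mean | Active mean | Placebo minus active | Simulated rejection |
|---|---|---|---|---|---|
| 54 h | 93 h | (2538 + 855.6)/56.2 = 60.4 | (2538 + 213.9)/49.3 = 55.8 | +4.6 h | about 10% |
| 24 h | 63 h | (2538 + 579.6)/56.2 = 55.5 | (2538 + 144.9)/49.3 = 54.4 | +1.1 h | about 5% |
| 10 h | 49 h | (2538 + 450.8)/56.2 = 53.2 | (2538 + 112.7)/49.3 = 53.8 | -0.6 h | about 5% |

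A positive value favours active treatment. Rejection rates come from simulated trials with gamma durations and a t test. Repeated runs of the 10 h case gave differences between -0.5 and -0.7 h. The sign changes where 39 + course = 54, that is, at a mean late course of 15 h.

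With a milder imbalance, 15% against 30% late starts and 54 h courses: placebo (2538 + 641.7)/53.9 = 59.0, active (2538 + 320.9)/50.45 = 56.7, difference 2.3 h. Simulated rejection is about 5.8%.

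**4. Delay with the plan's own effect.** 54 against 30 h, SD 30 h in both arms, 30% late starts in each arm (6.9 patients), onset 24 h later on active. Late score on placebo is 39 + 54 = 93 h, and on active 39 + 24 + 30 = 93 h. For these patients the delay cancels the shorter course. Expected difference = 24 x 47/53.9 = 20.9 h, against 24 h in patients on pressors at first dose. Simulated power falls from about 96% to about 87%.

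**5. Power if the set is restricted.** About 52 patients on pressors at first dose are needed, 52/140 = 37% of enrolment. By normal approximation, power is about 74% if 42 of 140 (30%) qualify, 85% if 56 (40%) and 97% if 94 (67%).

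**The case against.** The plan nowhere says that the analysed set is everyone ever on pressors. The allowance in the sample-size text could mean status at enrolment, and time to stopping a drug, counted from first dose, suggests that the drug is already running. That stands. A reader might infer that the plan selects its set by a post-randomisation event as a rule. The documents support only that the set is undefined and that the wording admits such patients.

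A reader might also infer that prevented shock will show up as faster weaning. That does not hold in general: the sign depends on the late starters' course length, which the documents do not give.

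A third inference would be that the randomised comparison is lost whenever late starters are included. It is not lost if treatment only delays onset and the late-start shares are equal. Treatment then does not change who enters, and the complaint is about what the score measures. Nor do the plan's own inputs support a severe loss of power: in the delay case above, power stays over the planned 80%.

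Finally, delta SOFA, the other primary end-point, is not conditioned on pressor use, and the hourly record should allow status at first dose to be derived. Both are true. They make the gap easy to close, but they do not supply the missing rule.

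**Conclusion.** The point holds. The written rule gives a late starter a score that is not time on pressors, and neither document says at what moment a patient must be on a pressor to be analysed. The scoring error follows directly from the definition. The selection problem is a consequence of the wording and not a stated rule.

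The size is uncertain. It rests on the share of patients on pressors at first dose, the late-start rates by arm, the onset times and the late course length, none of which is in the documents. Over the assumptions tried, the spurious difference ranges from about 4.6 h for active treatment to about 0.6 h against it. Error rates run from nominal to about 10%, and the higher figure needs both a strong imbalance in late starts and long late courses. Because the direction is unknown, a reader of the result could not correct for it. The definition should be settled before unblinding.

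**What to change.** State in the Primary end-point text of both Protocol and SAP that end-point i is analysed, by assigned arm, in all randomised patients receiving any vasopressor when the first dose of study drug or placebo starts. Take that status from the hourly vasopressor record (Data Collection, item viii).

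The moment should be the first dose and not randomisation, because the clock starts there. A patient weaned between the two would otherwise have no valid time, and one who starts pressors between them would be dropped. Status at the start of the first dose precedes any drug effect, and allocation is blinded, so the restriction should not depend on arm.

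Patients not on a vasopressor at that moment stay in delta SOFA and all secondary end-points. Report new vasopressor starts among them by arm, so that any preventive effect is visible.

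The cost is a few sentences in each document and no new data item if the hourly record is kept as planned. The downside is that late starters no longer count in end-point i, so the set shrinks by a number the documents do not give. The sponsor should check that about 52 patients on pressors at first dose can be expected among the 140.
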